26 APR 2024

Date

Sr. Director, Research Operations
The Romark Institute for Medical Research

Revision History

Version 1.2 to 1.3

1. Updated planned software from SAS to Python and related statistical packages (section 2.6).
2. Updated document ownership from [REDACTED] to Romark Institute for Medical Research.

Version 1.1 to 1.2

1. Changed the author and internal reviewer.
2. Added terms to list of abbreviations.
3. Added methods to handle missing data in the primary analysis.
4. Added further details to the interim analysis description.
5. Updated the demographic and baseline characteristic variables in Section 3.0.
6. Clarified the definition of an ARI to include the Suspected ARI Visit requirements.
7. Modified the primary analysis description to compute the common relative risk in place of the risk difference.
8. Renamed Table 14.2.1.9, added Table 14.2.1.10, and renumbered subsequent 14.2.1.x tables.
9. The following updates were made to align with Protocol Version 3.0, dated 27 August 2020:
 - a. Study title
 - b. Added 'social activities' as a stratum for most likely location of exposure
 - c. Changed the nasopharyngeal swab sample details
 - d. Changed description of Week 3 and 8 Evaluations to state that subjects will attend in-clinic visits
 - e. Modified sample size description to account for 6 strata
10. The following updates were made to align with Protocol Version 4.0, dated 28 September 2020:
 - a. Updated the strata so that 'social activities' stratum is now divided into social activities (3-5 per week) and social activities (> 5 per week), resulting in a total of 7 strata in the study.
11. The following updates were made to align with Protocol Version 5.0, dated 26 October 2020:
 - a. Modified sample size justification to reflect an event-drive approach

Version 1.0 to 1.1

1. Risk differences added to primary efficacy endpoint.
2. Section 2.2.2 Sex, Age, and Race subgroup analyses for primary efficacy endpoint added.
3. Sensitivity analyses added for missing values of primary efficacy variables.

Table of Contents

Approval Page	2
Revision History	3
Abbreviations and acronyms	5
1.0 Synopsis of Study Design Procedures	6
1.1 Design and Treatment.....	6
1.2 Study Procedures	6
Table 1: Clinical Illness Required for Diagnosis of ARI ¹ (adapted from Yu et al. 2020)	8
1.3 Sample Size.....	11
2.0 Data Analysis Considerations.....	11
2.1 Types of Analyses	11
2.2 Analysis Populations	12
2.3 Missing Data Conventions.....	12

1.0 Synopsis of Study Design Procedures

1.1 Design and Treatment

This is a multi-center, randomized, double-blind, placebo-controlled study to assess the safety and efficacy of Nitazoxanide (NTZ) for post-exposure prophylaxis of COVID-19, the viral respiratory disease caused by the novel coronavirus SARS-CoV-2 and other viral respiratory illnesses (VRIs) in healthcare workers and others at high risk of contracting SARS-CoV-2 infection. The study is a stratified two-arm study. The most likely location of exposure is being used as a proxy for SARS-CoV-2 exposure. The seven strata are:

- Emergency Department
- Intensive Care Unit
- COVID-specific Care Unit
- Walk-in Clinic
- Paramedics and First Responders
- Social Activities (3-5 per week)
- Social Activities (> 5 per week)

Participants will be randomized within strata (1:1) to one of

- Group I (NTZ)—Two 300 mg NTZ tablets orally b.i.d. (twice daily) for six weeks.
- Group II (Placebo)—Two placebo tablets b.i.d. (twice daily) for six weeks.

All participants will receive a B-complex vitamin () twice daily to mask potential chromaturia that may be associated with NTZ.

1.2 Study Procedures

Screening

Patients will be screened from Study Day -30 to Study Day 1. After giving informed consent, the subject will be assigned a subject number and complete the following procedures:

1. Survey of COVID-19 exposure.
2. Complete medical history.
3. Physical examination including body weight and vital signs (blood pressure, pulse, respiratory rate, and body temperature).
4. Collection of demographic information and smoking history.
5. Urine pregnancy test for all females of childbearing potential (must be performed Day 1).
6. Evaluation according to eligibility (inclusion and exclusion) criteria.

The information collected during the screening period must be current through the time of randomization.

Baseline

At Baseline (Study Day 1, which may be the same day as the screening evaluation) the subject will be randomized to Group I or Group II and complete the following procedures:

1. Collection of a nasopharyngeal swab sample using a single nylon flocked dry swab inserted into both nostrils for RT-PCR.
2. Collection of blood sample for laboratory safety tests and anti-SARS-CoV-2 antibodies.
3. Collection of a urine sample for routine urinalysis (appearance, glucose, protein, and blood).
4. Review and recording of any concomitant medications.
5. Provision of an electronic symptom diary to subject and subject completion of baseline electronic diary under supervision and instruction of study site personnel.
6. Randomization and dispensing of study medication (medication assigned in sequential order). Subjects are enrolled in the study at this point.
7. Administration of the first dose of study medication with food (< 1 hour after food intake) and a B complex vitamin ([REDACTED]) under observation of Investigator or a member of Investigator's staff, and entry in the medication administration record.
8. The subject will be instructed regarding the administration of study medication, completion of the electronic subject diary, use of birth control, follow-up visits at weeks 3, 6, 8, and on seeking emergency medical care or contacting the study physician or nurse under specific conditions.

CONTACT STUDY PHYSICIAN, IF:

- Trouble breathing including shortness of breath.
- Severe headache, stiff neck, confusion or excessive somnolence.
- If fever ($\geq 99^{\circ}\text{F}$ or $\geq 37.2^{\circ}\text{C}$) returns after being absent for 24 hours.
- Increased difficulty breathing.
- Wheezing develops.
- New pain develops or pain localizes to one area, such as an ear, the throat, the chest, or the sinuses.
- Symptoms become more severe or frequent.

- Symptoms recur or any difficulty breathing following 5-10 days resolution of illness.
- An allergic-like reaction occurs or is suspected.
- Abnormal behavior.

Study Weeks 1 through 6 (Daily)

Subjects will keep a daily diary to chart study medication and answer the question, “do you feel like you have symptoms of a cold or flu?” If the subject responds “yes”, they will be prompted to complete a full symptom diary questionnaire (FLU-PRO®) and contact the Investigator. A study physician, nurse or other designated site personnel will review each subject’s electronic diary entries daily to ensure compliance with collection of diary data. If a subject has not completed his/her diary or if errors are suspected, the study personnel will contact the subject to implement appropriate corrective actions.

If the subject reports (i) at least one of the Lower Respiratory Symptoms presented in Text Table 1 below or (ii) at least one symptom from each of the Upper Respiratory Symptoms and Systemic Symptoms categories presented in Text Table 1 below, the subject will then contact the study physician to complete a “Suspected ARI Visit” with the procedures provided below.

Table 1: Clinical Illness Required for Diagnosis of ARI¹ (adapted from Yu et al. 2020)

Upper Respiratory Symptoms	Lower Respiratory Symptoms	Systemic Symptoms

 • Nasal congestion/rhinorrhea (runny or dripping nose, congested or stuffy nose, head congestion, sinus pressure)² • Sore throat (sore or painful throat)² 	
 • Cough (coughing, chest congestion, chest tightness, dry or hacking cough, wet or loose cough)² • Dyspnea (shortness of breath)² • Sputum (coughing up sputum or phlegm)² • Wheezing 	
 • Myalgias or arthralgias (body aches or pains)² • Fatigue (weak or tired, sleeping more than usual)² • Headache • Decreased appetite (lack of appetite, did not feel like eating)² • Feverishness (felt hot, chills or shivering, felt cold, sweating)²

¹ Suspected ARI requires self-reporting of any Lower Respiratory Symptom, or at least one Upper Respiratory Symptom together with one Systemic Symptom.

² Lay language used in the FLU-PRO® questionnaire is presented in parentheses.

Suspected ARI Visit

Subjects reporting any lower respiratory symptom or at least one upper respiratory symptom and one systemic symptom are considered to have a suspected acute respiratory illness (ARI) and will complete the following procedures at an unscheduled Suspected ARI Visit.

1. Physical examination as warranted by the Investigator for any change from baseline.
2. Body weight and collection of vital signs to include blood pressure, pulse, respiratory rate, and body temperature.
3. Collect a nasopharyngeal swab sample using a single nylon flocked dry swab inserted into both nostrils for RT-PCR at the Suspected ARI Visit, 24 to 36 hours later, and then again 4 to 5 days later.
4. Collect a fecal specimen for RT-PCR at the Suspected ARI Visit, 24 to 36 hours later, and then again 4 to 5 days later.
5. The subject will complete a FLU-PRO[®] symptom diary daily until he/she responds "yes" to the FLU-PRO[®] question, "Have you returned to your usual health?" for 3 consecutive days or until the Week 6 Visit, whichever occurs first. The daily FLU-PRO[®] diary will be completed between 7:00 pm and 11:00 pm.
6. Review and recording of concomitant medications.
7. Review and recording of adverse events/side effects.
8. Laboratory investigations for safety may be performed as warranted based upon the Investigator's judgment.
9. Subjects testing positive for a respiratory virus by RT-PCR may receive standard of care as clinically warranted by the Investigator.

Regardless of symptoms or laboratory data, the subject will continue treatment until the 6-week treatment period has ended.

Week 3 (\pm 7 days) and Week 6 (\pm 2 days) Evaluations

Subjects will attend in-clinic visits at Week 3 and Week 6 and perform the following procedures:

1. Physical Examination as warranted by the Investigator for any change from baseline.
2. Body weight and collection of vital signs to include blood pressure, pulse, respiratory rate, and body temperature.
3. Collection of blood sample for laboratory safety tests, pharmacokinetics (pre-dose) and anti-SARs-CoV-2 antibodies (antibody testing at Week 6 visit only).
4. Collection of urine sample for routine urinalysis.

5. Review of compliance with study medication, collection of medication bottle with any unused medications (Week 6 visit only), and completion of the pill count log form.
6. Review and recording of concomitant medications.
7. Review and recording of adverse events/side effects and complications. Note that all adverse events and complications must be followed until their resolution or stabilization even beyond the 8-week study period.

Week 8 Evaluation (\pm 7 days)

Subjects will attend in-clinic visits at Week 3 and Week 6 and perform the following procedures:

1. Physical examination as warranted by the Investigator for any change from baseline.
2. Collection of blood sample for anti-SARs-CoV-2 antibodies.
3. Review and recording of concomitant medications.
4. Review and recording of adverse events/side effects and complications. Note that all adverse events and complications must be followed until their resolution or stabilization even beyond the 8-week study period.
5. Document any infections diagnosed during the follow-up period.

Other Unscheduled Visits

Subjects requiring an unscheduled visit due to worsening symptoms or adverse events will be evaluated at the discretion of the Investigator as is medically warranted. Tests and/ or procedures performed at this visit may include, but are not limited to, the following:

1. Physical examination as warranted by the Investigator for any change from baseline.
2. Body weight and collection of vital signs to include blood pressure, pulse, respiratory rate, and body temperature.
3. Collection of a nasopharyngeal swab sample using a single nylon flocked dry swab inserted into both nostrils for RT-PCR.
4. Collection of blood sample for laboratory safety tests.
5. Collection of urine sample for routine urinalysis.
6. Review of compliance with study medication.
7. Review and recording of concomitant medications.
8. Review and recording of adverse events/side effects.

2.0 Data Analysis Considerations

2.1 Types of Analyses

Data analyses will consist of analyzing patient characteristics, safety, and efficacy data.

2.2 Analysis Populations

2.2.1 Population Definitions

Subjects will be considered enrolled in the study upon completion of the baseline procedures. The following analysis populations will be used in the study.

- **Safety Population** – the safety population includes all patients who are enrolled in the study and that have received at least one dose of the assigned treatment arm (NTZ or placebo).
- **Intention-to-Treat Population (ITT)** – the ITT population includes all patients in the safety population who did not have a laboratory detected respiratory virus infection at the baseline visit.

The safety population will be used for all safety analyses. The ITT population will be the primary population for all efficacy analyses.

A data listing displaying the patients excluded from the ITT population will be created, as shown in the Table Requirements Document. This listing will be relative to all patients in the safety population.

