8.4.1. Efficacy Analyses

Efficacy analyses will be based on a population consisting of all subjects randomized without a laboratory-detected viral respiratory infection at the baseline visit (intention-

to-treat or ITT population). All chi-square analyses will be calculated with appropriate continuity corrections.

There will be two primary efficacy analyses:

- The proportion of subjects experiencing COVID-19 in the NTZ treatment group will be compared to that of the placebo treatment group using a two-sided Cochran-Mantel-Haenszel (CMH) chi-square test ($\alpha = 0.049$).
- The proportion of subjects experiencing VRI in the NTZ treatment group will be compared to that of the placebo treatment group using a two-sided CMH chi-square test ($\alpha = 0.001$).

Secondary analyses will be performed as follows:

- The proportion of subjects experiencing COVID-19 or VRI for treatment vs control will be tested within strata using Pearson chi-square tests at an unadjusted $\alpha = 0.05$.
- Confidence intervals (95% confidence level) will be produced for the overall odds ratio and for the odds ratios for NTZ vs placebo for each stratum.
- Proportions of subjects experiencing mortality due to COVID-19 or complications thereof will be compared by treatment group using a two-sided Pearson chi-square test (unadjusted $\alpha = 0.05$).
- Proportions of subjects (with or without symptoms) testing positive for antibodies to SARS-CoV-2 at either of the Week 6 or Week 8 visits will be compared by treatment group using a two-sided Pearson chi-square test (unadjusted $\alpha = 0.05$).

Exploratory analyses will be performed as follows:

- Proportions of subjects experiencing each of the following will be compared by treatment group using a two-sided Pearson chi-square test (unadjusted $\alpha = 0.05$): (i) hospitalization due to VRI or complications thereof, (ii) mortality due to VRI or complications thereof, (iii) proportions of subjects experiencing acute respiratory illness (ARI), (vi) hospitalization due to ARI or complications thereof, (v) mortality due to ARI or complications thereof.

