8.4.3. Safety Analyses

All randomized subjects who receive the study medication will be evaluated for drug safety. Safety analyses will be done descriptively.

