2.2.2 Subgroup Definitions

Certain efficacy analyses will be conducted on the various study strata. Efficacy analyses for the primary endpoints will be performed by sex (male/female), race (white/non-white), and age group (18- 34 years, 35- 64 years, and 65 year or older). Safety analyses will be grouped by treatment received.

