5.2 Description of Safety Analyses

Adverse Events

Adverse events will be graded by the investigator according to the “Guidance for Industry: Toxicity Grading Scale for Healthy Adult and Adolescent Volunteers Enrolled in Preventive Vaccine Trials” as adapted in the Study Protocol. The investigator will also assess causality (relationship to treatment) as *Definitely related*, *Probably related*, *Possibly related*, and *Unrelated*. AEs will also be coded using the Medical Dictionary for Regulatory Activities version 23 or higher (MedDRA®). Treatment-emergent AEs (TEAEs), defined as any AE that occurs after a patient receives the first dose of the assigned study treatment, will be summarized by the number and proportion of patients reporting at least one occurrence of the AE. Frequencies and rates of each TEAE will be summarized by MedDRA preferred term within system organ class (SOC), by severity grade, and relation to treatment for each treatment group. The rate calculation will be based on the number of patients in the Safety population for the relevant treatment group.

Treatment emergent serious adverse events (TESAEs) will be summarized and displayed by frequency and rate by MedDRA preferred term within SOC.

A by-patient AE data listing of all adverse events including verbatim term, coded term, grade, and relation to study treatment will be provided.

Laboratory Tests

Clinical laboratory tests will be performed at the times prescribed in the protocol. The following clinical laboratory tests will be analyzed:

Hematology:

Hemoglobin, hematocrit, complete white blood count (total and differential), platelet count, random blood glucose, total cholesterol, HDL, LDL, and triglycerides.

Clinical Chemistry:

AST, ALT, GGT, alkaline phosphatase, bilirubin (total and direct), BUN, creatinine, sodium, potassium, and chloride.

Urinalysis:

Appearance, glucose, protein, and blood.

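### SAP 2.2.1 makes a dose of the assigned arm a condition for both the safety and ITT populations, contradicting Protocol 8.4.1 and 8.4.3 and clashing with SAP 2.2.2

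*SAP*

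**What the plan says.** SAP 2.2.1 builds its two populations in sequence. The safety population is enrolled patients who "received at least one dose of the assigned treatment arm (NTZ or placebo"). The ITT follows from it: "the ITT population includes all patients in the safety population who did not have a laboratory detected respiratory virus infection at the baseline visit". The section adds that "The safety population will be used for all safety analyses", makes the ITT primary for all efficacy analyses, and bases the listing of ITT exclusions on the safety population.

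SAP 5.2 uses the same qualifier for treatment-emergent events: "any AE that occurs after a patient receives the first dose of the assigned study treatment". SAP 2.2.2, however, states: "Safety analyses will be grouped by treatment received".

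The protocol defines both sets without the qualifier. Its ITT in 8.4.1 is "all subjects randomized without a laboratory-detected viral respiratory infection at the baseline visit". On safety, 8.4.3 says: "All randomized subjects who receive the study medication will be evaluated for drug safety".

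**The concern.** The ITT should be fixed by randomisation and, in this trial, by the baseline swab. The SAP adds a post-randomisation condition, namely that the subject took the product allocated. The set that carries both primary tests is then narrower than the one in the protocol, and the SAP's revision history does not mention the change.

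For safety, the condition works against the purpose of the population. Someone exposed only to the other arm's product is exactly the person for whom treatment received and treatment assigned differ, and that person is not admitted. Events in a placebo-assigned subject who took only NTZ would appear in no safety table. Because the exclusion listing starts from the safety population, it would not show who was removed by the dosing rule.

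**Working it through.** **Step 1. Apply each definition literally.** The protocol columns follow 8.4.1 and 8.4.3; the SAP columns follow 2.2.1. Every subject is randomised and negative on the baseline swab.

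| Subject | Protocol ITT | SAP ITT | Protocol safety | SAP safety |
|---|---|---|---|---|
| Never dosed | in | **out** | out | out |
| Took only the other arm's product | in | **out** | in | **out** |
| Wrong kit number, assigned product inside | in | in | in | in |
| Mixed dosing, at least one assigned dose | in | in | in | in |

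The documents differ in the first two rows. The never-dosed subject is lost from the ITT only. The subject who took only the other product is lost from both sets.

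**Step 2. Can the second row occur?** Protocol 9.3 supplies one boxed kit of 180 tablets. At two tablets twice daily for 42 days the course needs 4 × 42 = 168 tablets, so one kit covers it. One mis-dispensed kit of the other arm can therefore mean that no assigned dose is ever taken.

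**Step 3. Follow that subject through the outputs.** In SAP section 8, all 14.3.x tables, the adverse event listing (16.2.7.1) and the deaths listing (16.2.7.2) are labelled Safety Population. The subject appears in none of them. Under SAP 5.2 the subject's events are not treatment-emergent either. Grouping by treatment received (SAP 2.2.2) comes too late, because it sorts only those already admitted.

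**Step 4. Missing-data rules.** SAP 4.2.1 keeps subjects with missing outcomes in the primary analysis, imputed as uninfected, and adds best-case, worst-case and tipping-point checks. A never-dosed subject is outside the ITT and never reaches these rules.

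**Step 5. Effect on power.** The documents give no rate of undosed or wrong-product subjects, so the rates here are assumptions. Inputs: 4,000 subjects, 1:1, placebo rate 1%, 80% reduction (NTZ 0.2%), two-sided alpha 0.049 (Protocol 8.1 and 8.4.1). Expected cases are 2,000 × 0.010 + 2,000 × 0.002 = 24. Power is from a two-proportion normal approximation.

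| Assumed exclusion from ITT | Subjects | Expected cases lost | Power |
|---|---|---|---|
| none | 0 | 0 | 90.5% |
| 0.5% | 4,000 × 0.005 = 20 | 24 × 0.005 = 0.12 | 90.3% |
| 2% | 4,000 × 0.02 = 80 | 24 × 0.02 = 0.48 | 89.9% |

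**Step 6. Effect of one excluded case.** With equal arms and, for simplicity, one stratum, the continuity-corrected statistic for a NTZ cases out of m is

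X² = (|a − m/2| − 0.5)² / V, with V = m(N − m) / [4(N − 1)] and N = 4,000.

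The critical value at alpha 0.049 is 3.875.

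- 7 of 24: V = 5.966, X² = 4.5²/5.966 = 3.39, p = 0.065. Not rejected.
- 6 of 24: X² = 5.5²/5.966 = 5.07, p = 0.024. Rejected.
- 6 of 23: V = 5.718, X² = 5²/5.718 = 4.37, p = 0.037. Rejected.
- 7 of 23: X² = 4²/5.718 = 2.80, p = 0.094. Not rejected.

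The cut-off is 6 or fewer NTZ cases at both 24 and 23 events. In the direction of benefit, losing one of the planned 24 therefore changes the conclusion only if the lost case is an NTZ case and the split was exactly 7 to 17.

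**The case against.** The strongest reply is that SAP 2.2.1 and 2.2.2 should be read together. The parenthesis naming both arms allows the ordinary meaning of any dose of study treatment, and grouping by treatment received mainly serves subjects whose product differed from allocation. On that reading the authors meant to keep them. This is plausible as to intent. It does not change the written rule, which SAP 5.2 repeats, and a programmer following 2.2.1 would drop these subjects before the grouping applies.

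Second, such cases should be rare. Randomisation is centralised, treatment numbers are on the box and bottles, and the first dose is taken under observation at the baseline visit. Failing to take it happens blind to arm, so removing undosed subjects should not bias the comparison. This stands, and it is why the point is of low severity.

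Third, exposure information would not vanish. Medication errors that cause adverse events are reported under Protocol 10.5, serious events go to the sponsor within 24 hours, and the disposition table covers all subjects. That is correct, but none of these is a safety analysis by arm.

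Fourth, the protocol's own ITT excludes baseline-positive subjects, so it is not a pure ITT either. That is true, but that exclusion rests on a baseline sample and is stated in both documents.

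**Conclusion.** The population rule in SAP 2.2.1 is wrong as written, with low severity. It contradicts Protocol 8.4.1 for undosed and wrong-product subjects and Protocol 8.4.3 for wrong-product subjects, and it is inconsistent with SAP 2.2.2. What is at stake is the meaning of the ITT label and the completeness of safety reporting, not power. Even an assumed 2% exclusion lowers power by 90.5 − 89.9 = 0.6 points.

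A reader might infer more than the documents support:

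- That any wrong-kit subject drops out. Only a subject who never took an assigned dose does.
- That undosed subjects are removed from safety against the protocol. Protocol 8.4.3 does not include them either.
- That a definite number leaves both populations. No rate is given, and only subjects who took solely the other product could leave both.
- That losing any one case threatens the primary result. It does so only at the boundary shown above.

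The conclusion on wording rests on the literal text. The conclusion on size rests on the observed first dose, the assumed exclusion rates and the plan's assumed illness rates.

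**What to change.** Change the SAP wording as follows:

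- **2.2.1, ITT:** all randomised subjects without a laboratory-detected respiratory virus at baseline, analysed as randomised.
- **2.2.1, safety:** all randomised subjects who took at least one dose of any study medication, grouped by treatment received. Naming randomisation rather than enrolment also avoids a side issue: SAP 1.2 places enrolment at randomisation and dispensing, while 2.2.1 places it at completion of the baseline procedures, which include the first dose.
- **5.2, treatment-emergent event:** an adverse event after the first dose of any study medication.
- **2.2.1, exclusion listing:** base it on all randomised subjects and give the reason for each exclusion.

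The cost is SAP text and the matching population flags in the analysis programs. Design, sample size and data collection do not change.
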